11.4 Follow-up of Adverse Events

Subjects will return to the clinical site for a 24-hour follow-up safety assessment which will include an assessment of AEs. Any AE that is on-going at the time of the 24-hour follow-up assessment will be followed by the investigator until resolution or until the principal investigator and the Medical Monitor agree that further follow-up is no longer clinically relevant.

If subjects do not return for the 24 hour safety assessment, a follow-up telephone contact for AE resolution assessment must be documented on the CRF and in subject records, including

date, time and summary of conversation.

11.5 Procedures for Reporting AEs, SAEs and Suspected Unexpected Serious Adverse Reactions (SUSARs)

All AEs spontaneously reported by the subject and/or in response to an open question from study personnel or revealed by observation, physical examination or other diagnostic procedures will be recorded on the AE section of the CRF. Any clinically relevant deterioration in laboratory assessments or other clinical findings is considered an AE must be recorded on the AE section of the CRF.

All AEs will be noted and evaluated on the CRF with a full description of the nature, onset, duration, severity, attribution, and outcome of the event. All AEs will be coded using MedDRA. Any treatment used to alleviate the AE(s) will also be recorded.

Adverse event recording and reporting will conform to International Conference on Harmonisation (ICH) of Technical Requirements for Registration of Pharmaceuticals for Human Use Guidelines for Clinical Safety Data Management.

When possible, signs and symptoms indicating a common underlying pathology should be noted as one comprehensive event. All AEs should be recorded using standard medical terminology.

All SAEs that occur during the course of the study, as defined by the protocol, must be reported immediately by the investigator to the Medical Monitor by telephone or fax within 24 hours of the time the investigator first becomes aware of the SAE. Such preliminary reports should be followed with a detailed written description (within 5 days) which will include copies of hospital records and other documents when applicable.

All SAEs must be reported whether or not considered causally related to the study product. An SAE form will be provided to each clinical study site.

The investigator is required to document in full the course of the SAE, including any therapy given to the subject. The information collected will include, at a minimum, the following: subject number, description of the event and an assessment by the investigator as to the severity of the event and relatedness to study product. Follow-up information on the SAE may be requested by Cyclomedica. The SAE must also be recorded on the AE section of the CRF.

The investigator will also inform the sponsor of any relevant follow up information and the outcome of the SAE as soon as possible in a follow-up report.

Medical Monitor Contact Information:

11.5.1 Suspected Unexpected Serious Adverse Reaction (SUSAR)

The Sponsor must submit an Investigational New Drug (IND) Safety Report to the United States Food and Drug Administration (FDA) for any suspected adverse reaction that is both serious and unexpected. Before submitting the report, the sponsor will need to ensure that the event meets the following criteria:

- Suspected adverse reaction
- Serious
- Unexpected

If the AE does not meet all three of the definitions, it should not be submitted to the FDA in an IND Safety Report. The Sponsor, with input from the Medical Monitor, will evaluate the information and decide if there is a reasonable possibility that the drug caused the AE and therefore meets the definition of suspected adverse reaction. Reasonable possibility means there is evidence to suggest a causal relationship between the drug and the AE.

A written IND Safety Report must be submitted to FDA within 15 calendar days since the determination that the suspected adverse reaction or any other information qualifies for reporting.

Unexpected fatal or life-threatening suspected adverse reactions must be reported to FDA in an expedited report no later than 7 calendar days after the Sponsor's initial receipt of information.

12 Schedule of Efficacy and Safety Assessments

12.1 Visit 1

During Visit 1, screening procedures are performed, informed consent is obtained and documented with signature and date, and eligible subjects are enrolled. The investigators will be asked to record the purpose for a subject's Xe-133 ventilation imaging, and based on their recent chest X-ray indicate whether pleural effusion is present for the subject.

Subjects will undergo Xe-133 ventilation imaging. This will be followed as soon as practical by the Technegas imaging procedure. Because of the rapid clearance of Xe-133 from the lungs and the low, non-interfering energy of Xe-133 photons, a washout period is not required.

The Sponsor must be notified if Xe-133 and Technegas imaging sessions are to be performed in separate visits. The Sponsor will grant approvals only on a case-by-case basis. If the second imaging procedure must be done during a separate visit occurring within 24 hours of the first visit, this will result in an additional visit for the subject.

If a Tc-99m MAA perfusion study is planned for the subject as part of their standard of care at this visit, it must occur after Technegas imaging is complete, and after the post-Technegas imaging safety assessments, within 15 minutes post-imaging, have been captured.

12.2 Visit 2

Subjects will be asked to return to the clinical site 24 (20-36) hours after completing Technegas planar ventilation imaging for a complete safety assessment, including clinical laboratory evaluation.

If the subject does not return for the 24-hour safety assessment, the subject must be contacted by the Principal Investigator at approximately 24 hours by telephone and interviewed for emergent AEs. The telephone contact and results will be documented on the CRF and in subject records, including date, time and summary of conversation. In addition, it should be documented as a protocol deviation, and the subject will be considered incomplete with respect to safety assessments.

12.3 Schedule of Efficacy and Safety Assessments

	Visit 1							Visit 2
	Screening	Xe-133			Technegas			24-hour (20-36) Follow-up
		Prior to Inhalation (≤30 min.)	Ventilation and Imaging	Post- Imaging	Prior to Inhalation (10 ± 5 min.)	Ventilation and Imaging	Post- Imaging (≤ 15 min.)	
	Baseline							
Inclusion/Exclusion	x							
Informed Consent	x							
Demographics	x							
Pregnancy Test	x							
Medical History	x							
Physical Exam	x						x	
Chest X-ray	x							
Clinical Labs	x						x	
Vital Signs		x		x	x		x	
Oxygen Saturation		x		x	x		x	
Ventilation Imaging			x			x		
Adverse Events	x	Monitored throughout the study						x
Concomitant Medication	x	Monitored throughout the study						x

13 Statistical Analysis

13.1 General Considerations

The primary presentations and analyses will be based on data pooled across study centers. Relevant summaries for individual centers, or combinations of centers, also may be presented for primary data. Standard descriptive statistics will be used to summarize data, including one- and multi-way frequency tables for discrete or categorical variables, and mean, median, standard deviation, minimum, maximum for continuous variables.

All data collected and entered into the study database will be provided in data listings by variable type presenting individual subject values. All testing and confidence intervals will use a two-sided significance level of 5%, unless otherwise specified.

Additional details concerning the planned statistical methodologies are provided in the Statistical Analysis Plan.

13.2 Analysis Populations

Three analysis data sets will be defined for the study:

- Modified Intent-to-Treat (MITT) Set will consist of all subjects who are enrolled in this study and receive any dose of Technegas treatment; it will be the analysis set for the safety analyses.
- Full Analysis Set (FAS) will consist of subjects who completed all of the ventilation imaging on the study, and both sets of Xe-133 planar scans and the Technegas planar scans are of interpretable image quality according to site investigators' assessment.
- Per Protocol Set (PPS) will consist of those subjects in the FAS who are compliant with regard to the Technegas and Xe-133 procedures (dosing and imaging), and have no other major protocol violations.

13.2.1 Disposition

Subject disposition will be summarized and will include:

- Number of subjects screened
- Number of subjects enrolled in the study
- Number of subjects included in the MITT set
- Number of subjects withdrawn from the study and the reason for withdrawal
- Number of subjects in the FAS
- Number of subjects in the PPS

The screening data for all subjects who were screened but not enrolled into the study will be provided in a separate data listing. These subjects will not be included in any other listings, tabulations, or analyses.

13.2.2 Baseline Characteristics

Demographic data, including age, gender, race, ethnic group, and reason for ventilation imaging will be summarized using descriptive statistics.

Abnormal medical histories and prior/concurrent medications will be summarized using counts and percents. Prior/concurrent medications will be coded using the World Health Organization (WHO) classification system. Prior and concurrent medication use overall and by WHO medication classification will be summarized using counts and percentages.

13.3 Efficacy Evaluations

13.3.1 Primary Efficacy Endpoint

The primary efficacy endpoint is percent agreement between Technegas and Xe-133 obtained from each blinded reader's ventilation scores of matching image views.

The agreement statistic will be derived from the ventilation scores as follows. Binary agreement scores will be obtained for each subject's six lung regions: if the Technegas and Xe-133 ventilation scores are the same for a lung region, the region is assigned an agreement score of 1, otherwise the region is assigned a score of 0 for no agreement. The subjects' binary agreement scores will provide the basis for an overall estimate of percent agreement and confidence interval for each of the three readers.

In the case of a missing ventilation score (score = 99) as a result of a reader assessing a region as obscured or absent, the binary agreement score will be determined as follows. If both Technegas and Xe-133 scores are missing for the region, the binary agreement score will be missing for the region. If the score is missing for one of the imaging modalities and not the other, then the region will be assigned a score of 0 for no agreement.

13.3.2 Secondary Efficacy Endpoints

Secondary efficacy endpoints include:

1. Percent agreement between Technegas and Xe-133 obtained from blinded readers' ventilation scores based on all image views collected for Technegas and Xe-133.
2. Percent agreement between Technegas and Xe-133 for the subgroups of subjects with and without pleural effusion as noted in subjects' chest X-rays, from blinded readers ventilation scores.

3. Percent agreement measuring inter-observer agreement between pairs of blinded readers for their Technegas ventilation scores, and for their Xe-133 ventilation scores.
4. By lung-region kappa statistics measuring inter-observer agreement between pairs of blinded readers for their Technegas ventilation scores, and for their Xe-133 ventilation scores.

13.4 Efficacy Analyses

13.4.1 Primary Efficacy Analyses

The primary analysis will be conducted on the FAS for Technegas and Xe-133 matched image views. Each blinded readers' binary agreement scores will be analyzed using a generalized linear model with SAS® PROC GENMOD. The logit function (log odds ratio) will be specified as the link function, and subject will be specified as a repeated measure to allow for correlations between lung regions within a subject. The estimate of the intercept of the model using generalized estimating equation (GEE) methodology will provide an overall estimate of the agreement and its 95% confidence interval in terms of the log odds ratio; simple algebra will be used to obtain the corresponding estimates and confidence intervals in terms of percent agreement (PA).

The non-inferiority hypothesis to be tested is:

$$H_0: PA \leq 60\% \text{ versus } H_A: PA > 60\%$$

If the lower boundary from the 95% confidence interval for PA is greater than 60%, Technegas will be considered non-inferior to Xe-133 with respect to the measurement of pulmonary ventilatory distribution.

Study Success Criteria

For the study to be deemed a success, the null hypothesis must be rejected for at least two of the blinded readers.

13.4.2 Secondary Efficacy Analyses

The same methodology as described for primary efficacy analyses in the previous section will be applied to the binary agreement scores between Technegas and Xe-133 obtained from blinded readers' ventilation scores based on all image views, both for the FAS and PPS analysis datasets. The methodology will also be applied to the agreement scores between Technegas and Xe-133 for the subgroups of subjects with and without pleural effusion.

Inter-reader percent agreement between pairs of blinded readers Technegas ventilation scores and their 95% confidence intervals will be obtained using the same methodology described for the primary efficacy endpoint. Analyses will be performed for both FAS and PPS. For comparison, the inter-reader percent agreement will be obtained in the same manner for Xe-133 ventilation scores.

By lung region, inter-reader kappa statistics and their 95% confidence intervals will be calculated for pairs of blinded readers using the three by three tables of the frequencies of ventilation scores for Technegas as displayed:

Ventilation Score Reader I	Ventilation Score Reader J		
	0	1	2
0	N ₀₀	N ₀₁	N ₀₂
1	N ₁₀	N ₁₁	N ₁₂
2	N ₂₀	N ₂₁	N ₂₂

where N_{ij} represents the agreement frequency for a cell. For comparison, the by-region inter-reader kappas based on the blinded readers' ventilation scores for Xe-133 scans will also be obtained.

13.5 Non-Inferiority Margin

The non-inferiority margin used in the analysis of the primary endpoint of this study was principally determined from a separate study conducted under Protocol CYC-010. In Study CYC-010, six blinded readers read 75 Xe-133 planar ventilation imaging studies in two read sessions separated by a minimum of 4 weeks. The readers scored the six regions of the lung using the same ventilation scoring metric to be used in this protocol. The two sets of assessments from the read and re-read of the Xe-133 images were used to determine a measure of agreement between successive reads of Xe-133 lungs scans for each of the readers, and the compilation of the six readers' estimates were then used to establish a 95% tolerance interval for the population of readers. The lower bound of the tolerance interval was 62%. Since Xe-133 is an approved agent for ventilation imaging, it by default is considered non-inferior to itself, and hence the read/re-read results provide a suitable limit for establishing the non-inferiority of Technegas compared to Xe-133.

When comparing Xe-133 and Technegas imaging, it is recognized that there are inherent differences between the imaging performed with Xe-133 and Technegas: Xe-133 imaging includes both wash-in and wash-out views, while Technegas imaging has no equivalent to the wash-in/wash-out views but collects additional views. This has the potential to result in differences in ventilation scoring which are not clinically relevant. For example, in subjects that have regions of pleural effusion, on Xe-133 the region would likely be scored as 1=decreased ventilation based on retention visible in wash-out views, whereas on Technegas it would be scored as 0=absent ventilation. Only a small percentage of subjects are expected to exhibit such discrepancies and to account for this, a small adjustment was made to the non-inferiority margin obtained from the CYC-010 study from 62% to 60%. The anticipated

agreement between Technegas and Xe-133 imaging is 70%. The standard error of the agreement for the Xe-133 to Xe-133 image comparison among the six readers from study CYC-010 was 4.6% and thus a lower confidence interval bound of 2 standard errors also supports a non-inferiority margin of about 60%. Thus the non-inferiority margin planned for this study is 60%.

13.6 Rationale for Sample Size

Using the normal approximation to the binomial distribution for calculation of the sample size, and the proportion associated with the non-inferiority margin (P0) to estimate the standard deviation, the following table provides sample size requirements for testing the hypotheses:

$$H_0: PA \leq P_0 \text{ versus } H_A: PA > P_0$$

where PA (percent agreement) has expected true values of 70% to 75%, and the non-inferiority margin (P0) is 60%.

Table Sample Size for 90% Power and 0.025 One-sided Type 1 Error

Non-inferiority Margin P0 (%)	Expected True Value PA (%)	Required Sample Size (N)
60	70	240
	71	197
	72	164
	73	139
	74	119
	75	103
Calculations performed with PASS 14 ¹²		

The planned sample size for the study is 240 subjects who have completed Xe-133 and Technegas ventilation imaging, and the images are of interpretable quality (FAS). This sample size will provide 90% power to establish that agreement between the blinded read assessments of Xe-133 and Technegas is better than 60%, assuming an expected true level of agreement between Xe-133 and Technegas of 70%.

13.7 Interim Analysis

After approximately 40 subjects have completed the study, an interim pilot blind read of the Xe-133 and Technegas ventilation images will be conducted to assess the viability of the planned efficacy measurements for comparing the two sets of images. If it is determined that the initial study design and efficacy parameters are not viable due to the differences in the

image sets being acquired, the protocol will either be amended in accordance with Agency input, or the study may be terminated. The readers performing the pilot blind read will not be used for the final blind read of images, and unless imaging parameters change, the images from these first 40 subjects will be included in the final read of images.

13.8 Safety Endpoints

Safety endpoints include:

1. Incidence of treatment emergent AEs.
2. Changes (24 hours post-Technegas minus baseline) in laboratory measurements. The laboratory measurements at screening will serve as the baseline.
3. Incidence of clinically significant changes in laboratory measurements.
4. Change (post minus baseline) in vital signs at each time-point post Xe-133 and Technegas administration. The measurements within 30 minutes prior to Xe-133 inhalation will serve as the baseline.
5. Incidence of clinically significant changes in blood pressure (defined Section 11.2.3).
6. Change (post minus baseline) in oxygen saturation at each time-point post Xe-133 and Technegas administration. The measurements within 30 minutes prior to Xe-133 inhalation will serve as the baseline.
7. Incidence of treatment emergent abnormalities in physical examinations.

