4.6 Treatment Compliance

Trained clinical staff will be responsible for initiating and completing Technegas administration and ventilation imaging. The trial will be conducted in compliance with this protocol, Good Clinical Practice (GCP) guidelines and applicable regulatory requirements.

5 Study Objectives and Purpose

The primary objectives and purpose of this study are:

1. To demonstrate the non-inferiority of Technegas compared to Xenon 133 (Xe-133) ventilation studies, using planar scintigraphic imaging, with respect to their pulmonary ventilatory distribution in subjects that are candidates for ventilation imaging.
2. To assess the safety profile of Technegas by monitoring AEs, clinical laboratory measurements (blood chemistry and hematology), pulse oximetry, and vital signs pre- and post-Technegas administration.

6 Trial Design

This is a Phase 3 within-subject non-inferiority trial of Technegas ventilation planar imaging compared to Xe-133 ventilation planar imaging. Subjects will be males and females at least 18 years of age who have been referred for ventilation scintigraphy for any medical reason. Subjects will have undergone a chest X-ray, and during the study will undergo planar Xe-133 imaging followed by planar Technegas imaging.

Xe-133 images will be obtained per site-specific standard of care at each investigational site, which most commonly is posterior/posterior oblique image views or anterior/posterior image views collected during wash-in and wash-out. Technegas images will include a six view image set: anterior, posterior, LPO, RPO, LAO, and RAO views.

Enrollment will continue until 240 subjects have completed the study. This number of subjects is expected to provide 90% power for demonstrating the non-inferiority of Technegas compared to Xe-133 in the assessment of ventilation imaging. The non-inferiority margin to be used in this study was primarily determined from a separate study conducted under Protocol CYC-010.

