6.2 Randomization and Blinding

This is an open-label, non-randomized clinical trial. All subjects will undergo Xe-133 planar imaging and Technegas planar imaging. Subjects will undergo Xe-133 inhalation and imaging first, followed by Technegas inhalation and imaging as soon as practical and no longer than 24 hours after completing the Xe-133 imaging. Because of the rapid clearance of Xe-133 from the lungs and the low, non-interfering energy of Xe-133 photons, a wash-out period is not required.

While the Xe-133 will not interfere with the Technegas images, it is recognized that there will be potentially confounding effects of Xe-133 and Technegas on safety parameters.

The primary efficacy data will be from a blinded read managed by Certus International, a contract research company and imaging core lab located in Bedford, NH and St. Louis, Missouri. Three experienced nuclear medicine physicians will be selected to perform independent blinded reads. The readers will have experience reading Xe-133 ventilation images, as well as experience reading DTPA ventilation scans. Like Technegas, DTPA is a particulate based ventilation imaging agent. Training in reading Technegas scans will also be provided. Each reader will independently assess both the Xe-133 images and the Technegas images in separate sessions. Each image set will be assigned a unique random code number, which will govern the order in which the subjects' images are read. The readers will be shown a recent anteroposterior or posteroanterior chest X-ray of the lungs but will be blinded to subject identity, reason for the ventilation scan, results of procedures and to any other subject information.

Additional details on the blinded read are provided in the Imaging Charter.

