7.3 Withdrawal or Termination of Participation

Every subject has the right to terminate his or her participation in the study at any time without providing reasons. A subject's participation will terminate immediately upon his/her request.

A subject who signs the informed consent form, but discontinues study participation without inhaling Technegas is termed a withdrawn subject. Subjects may withdraw themselves or may be withdrawn by the investigator. Data collection for withdrawn subjects will cease at the time of their withdrawal.

Subjects may withdraw or be withdrawn for any of the reasons listed below:

- Did not meet inclusion/exclusion criteria
- Withdrew consent
- Lack of compliance with study procedures
- Investigator decided it is in the subject's best interest to be withdrawn

A subject who signs the informed consent form and then undergoes Technegas inhalation, but does not complete all of the imaging procedures and/or all of the safety assessments including clinical laboratory evaluation, is termed an **incomplete subject**.

Whatever the reason for lack of study completion, the investigator should attempt to collect and report the required Technegas safety data.

A subject who meets all inclusion criteria and no exclusion criteria, undergoes Technegas inhalation and completes all study procedures is termed a **complete subject**.

8 Treatment of Subjects

Subjects will undergo Xe-133 and Technegas inhalation and imaging. Safety will be monitored pre- and post-inhalation of Technegas by assessing changes in clinical laboratory measurements, vital signs, blood oxygen saturation by pulse oximetry, and physical examination.

Subjects must agree to return for an in-person 24-hour follow-up after Technegas inhalation to obtain safety assessments. Prior to enrolling the subject, the required 24-hour follow-up safety assessment will be discussed with the patient and documented. Subjects that agree to return for the 24-hour follow-up and sign the informed consent form will be entered into the study.

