11.2.3 Vital Signs

Vital signs must be obtained and recorded, including:

- Systolic and diastolic blood pressure millimeters of mercury (mm Hg)
- Pulse rate (beats/minute)
- Respiratory rate (breaths/minute)

The same position and arm should be used each time vital signs are measured for a given subject.

Vital signs will be collected within 30 minutes prior to the Xe-133 imaging study. These will be considered baseline measurements. Additional vital signs will also be taken following completion of the Xe-133 imaging, but prior to Technegas imaging.

Vital signs will be taken at approximately 10 minutes (\pm 5 minutes) prior to Technegas inhalation and within 15 minutes following completion of the Technegas imaging. Additional vital signs will be taken during the 24-hour follow-up safety assessment.

The following changes (increases or decreases) in vital signs from pre-study baseline values are considered to be clinically significant and require commentary:

- systolic blood pressure > 45 mm Hg
- diastolic blood pressure > 30 mm Hg

Any clinically significant worsening changes will be documented on the AE page of the CRF.

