13.9 Safety Analyses

The summary and analysis of safety data will be conducted on the modified ITT dataset.

Frequency distributions including counts and percentages will be used to summarize the qualitative safety data, including AEs, clinically significant changes in laboratory measurements and vital signs, and treatment emergent abnormalities in physical examinations. The summary of AEs will include summaries by MedDRA system organ class, relationship to study treatment, and event severity. Serious adverse events also will be summarized separately.

Summary statistics will be provided for all continuous safety data including change in laboratory measurements, vital signs and oxygen saturations. Paired t-tests will be used to test for statistically significant changes over time. The laboratory measurements at baseline and follow-up also will be categorized relative to their reference ranges as low, within range, or high, and shift tables comparing the distributions from baseline to follow-up will be provided for each test. The Stuart Maxwell test will be used to test for statistically significant changes in pre- versus post-treatment distributions.

14 Data Handling and Record Keeping

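### Post-Technegas vital-sign and oxygen-saturation changes are measured from the pre-xenon reading, and no supplied document specifies the paired change across the Technegas interval

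*Combined protocol and SAP*

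**What the plan says.** Protocol 13.8, item 4, defines the vital-sign endpoint: "Change (post minus baseline) in vital signs at each time-point post Xe-133 and Technegas administration". Item 6 does the same for oxygen saturation. Both fix the reference: "The measurements within 30 minutes prior to Xe-133 inhalation will serve as the baseline". Item 5 counts clinically significant blood-pressure changes as defined in 11.2.3, which measures them from the pre-study baseline and identifies baseline as the reading before xenon.

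On analysis, 13.9 gives summary statistics and adds: "Paired t-tests will be used to test for statistically significant changes over time". It does not name the pairs of time-points. Section 13.1 leaves further detail to the SAP. Of the SAP, only the addendum is supplied; it deals with the interim efficacy analysis and specifies no vital-sign or saturation analysis.

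Other sections describe safety around Technegas itself. Objective 2 (section 5) covers "pulse oximetry, and vital signs pre- and post-Technegas administration". Section 8 says: "Safety will be monitored pre- and post-inhalation of Technegas by assessing changes in clinical laboratory measurements, vital signs". Section 6.2 accepts that "it is recognized that there will be potentially confounding effects of Xe-133 and Technegas on safety parameters".

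Readings that bracket Technegas are collected. Section 11.2.3 has one after xenon imaging ("Additional vital signs will also be taken following completion of the Xe-133 imaging, but prior to Technegas imaging"), one shortly before inhalation ("Vital signs will be taken at approximately 10 minutes", ± 5 minutes), and one within 15 minutes after Technegas imaging. Section 11.2.4 sets the same times for saturation. Under section 12, any perfusion study waits until the last of these has been captured.

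**The concern.** Xenon is given first in every subject and there is no control group. A change measured from before xenon to after Technegas therefore cannot say in which of the two intervals it arose. A xenon-period shift can show up as a significant post-Technegas change, and an opposite shift can hide a real one. The protocol recognises this confounding and collects the reading that would split the two intervals, but the supplied documents name no analysis that pairs that reading with the one after Technegas. At stake is how the descriptive safety tables for Technegas are read, not the efficacy conclusion.

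**Working it through.** **Which contrasts are planned.** Let A be the pre-xenon reading, B the 10 ± 5 minute pre-Technegas reading, and C the reading within 15 minutes after Technegas imaging.

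- Items 4 and 6 cover every time-point after xenon and after Technegas, each against A. B is a time-point after xenon, so B − A is planned, and so is C − A.
- C − A = (B − A) + (C − B): xenon-period change plus Technegas-interval change.
- C − B is named nowhere in the supplied documents. The wording of 13.9 would allow it but does not specify it.

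**What the planned tables give.** On the same subjects, mean(C − B) = mean(C − A) − mean(B − A), so the mean can be derived exactly. The SD cannot, because it needs the correlation ρ between the two changes. With equal SDs s, SD(C − B) = s√(2(1 − ρ)). For an assumed s = 10, this is 14.1 at ρ = 0, 10.0 at ρ = 0.5 and 4.5 at ρ = 0.9. The subject listings in 13.1 would allow it to be computed, but it is not a planned summary.

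**How much it could matter.** The plan has no figure of its own to reproduce here. From the documents come n = 209 (225 enrolled less 16 withdrawn before Technegas; addendum section 2) and n = 240 (planned). The documents give no xenon effect, SD or correlation, so these are assumptions:

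- d: xenon-period shift, in SDs of change;
- r: the fraction of that shift recovered between B and C;
- ρ = 0.5 unless stated, so that all SDs are equal;
- a true Technegas effect of zero.

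Then mean(C − A) = d(1 − r) and mean(C − B) = −rd. Each is tested by a two-sided 5% paired t-test, whose power follows from the noncentral t with noncentrality (mean/SD)√n. For d = 0.20 and r = 0, the noncentrality of C − A is 0.20 × √209 = 2.89, or 0.20 × √240 = 3.10.

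Probability of a significant result, d = 0.20:

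| r | C − A, n=209 | C − B, n=209 | C − A, n=240 | C − B, n=240 |
|---|---|---|---|---|
| 0 | 0.82 | 0.05 | 0.87 | 0.05 |
| 0.25 | 0.58 | 0.11 | 0.64 | 0.12 |
| 0.5 | 0.30 | 0.30 | 0.34 | 0.34 |
| 0.75 | 0.11 | 0.58 | 0.12 | 0.64 |
| 1 | 0.05 | 0.82 | 0.05 | 0.87 |

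- **Smaller shift.** With d = 0.10 persisting (r = 0), C − A is significant 30% (n=209) or 34% (n=240) of the time.
- **Other correlations.** At r = 1, with ρ from 0.3 to 0.7, C − B is significant 68% to 96% of the time at n=209 and 74% to 98% at n=240.
- **Half recovery.** The 30% to 34% applies to each contrast alone. The two contrasts are positively correlated (0.5 in this model), so both being significant in opposite directions happens only about 3% (n=209) to 5% (n=240) of the time.

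**Cost in tests.** There are five variables: systolic and diastolic pressure, pulse, respiratory rate and saturation. If independent, the chance of at least one false positive is 1 − 0.95⁵ = 0.226; the upper bound is 5 × 0.05 = 0.25.

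**The case against.** The strongest reply is that the baseline is declared and consistent. Section 6.4 ends the safety baseline period before xenon. Objective 2 applies its pre- and post-Technegas wording to laboratory tests as well, and their only earlier value is the screening one, also before xenon. A reader might infer that 13.8 contradicts objective 2; it does not, because a pre-xenon value is also a pre-Technegas value. The point is that a useful contrast is unspecified, not that the chosen baseline is wrong.

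A reader might also infer that the pre-Technegas reading goes unused. It does not: items 4 and 6 summarise it against the pre-xenon baseline. Nor can it be said that the contrast is absent from the plan as a whole, since 13.9 leaves its pairs open and SAP Version 2 is unseen.

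Other routes to attribution exist. Adverse events before Technegas count as pre-treatment (11.3), events are summarised by relationship (13.9), and saturation below 90% is attributed by the investigator, with a code for the xenon procedure (11.2.4). These stand and limit the importance of the point. They do not give the size or precision of the average change across the Technegas interval.

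The illustration is also symmetric: under full recovery the added contrast is the misleading one. That stands too. It argues against replacing the planned contrast, and for showing both.

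Finally, it is tempting to apply the item 5 blood-pressure thresholds to the new contrast. The documents do not support this, because 11.2.3 ties those thresholds to pre-study baseline values.

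**Conclusion.** The point holds as a modest, inexpensive improvement. Items 4 and 6, and item 5 through 11.2.3, use the pre-xenon reference. No analysis named in the supplied documents takes the pre-Technegas reading as reference, so the planned post-Technegas change mixes two intervals that the collected data could separate. What is unspecified is the SD, confidence interval and test of the Technegas-interval change; its mean is derivable.

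The probabilities rest on assumed shifts, recovery and correlation. They show that either contrast can mislead where the other does not; they are not evidence that xenon shifts these measurements. Statistical significance at these sample sizes does not imply clinical relevance. No success criterion uses these tests: success under 13.4.1 depends on reader agreement alone. Confidence is medium, mainly because SAP Version 2 may already contain the contrast.

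**What to change.** First check SAP Version 2. If it already specifies the contrast, a cross-reference is enough. If not:

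- Add to 13.8 and 13.9 the paired change from the 10 ± 5 minute pre-Technegas reading to the reading within 15 minutes after Technegas imaging, for vital signs and oxygen saturation. Give summary statistics and a 95% confidence interval, with any paired test labelled descriptive.
- Report it beside the pre-xenon contrast, not in its place.
- State which pairs of time-points the t-tests in 13.9 compare.
- Leave the item 5 thresholds on their stated pre-study baseline.

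The cost is SAP wording and a few tables from readings already collected, with no effect on efficacy or alpha. The downsides are two baselines that need clear labels and about five more unadjusted descriptive tests. If adopted at the addendum stage, the contrast must also be labelled as a late addition, because 209 subjects are complete and an interim safety report has already gone into the NDA.
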